## 8.0 Statistical Considerations

In this study, we will evaluate the dosages received by tumors and surrounding tissue using PET-CT data. The primary objective is to determine the relationship between radiation dose to 70% of the tumor volume and local control at 6 months. We will conduct this analysis at the tumor level, as different tumors may receive different doses of radiation, and may have different progression statuses at 6 months. We will use standard summary measures such as means, medians, ranges, and standard deviations to characterize the dosages received by tumor and other tissue. We will use percentages and frequency tables to evaluate other characteristics such as tumor histology, number of liver tumors per patient, and volume of liver tumors.

We will determine the relationship between radiation dose and local control at 6 months using regression models with Generalized Estimating Equations (GEE) to account for within-patient correlation. We will use logistic regression to adjust for potentially confounding factors such as tumor volume, primary histology, and SIR-Spheres versus Therasphere intervention. We will also determine the relationship between radiation dose to healthy tissue, and side effects such as fatigue, nausea, pain and elevated liver function tests. Each

side effect will be characterized as present or absent, and we will test the relationship between radiation dose to the relevant type of healthy tissue and each side effect. For example, we will look at the relationship between dose to the normal liver and elevation of liver function tests.

In further secondary analyses, we will explore the relationship between the distribution of activity measured by PET-CT, and the distribution predicted by T-99m labeled MAA. This can be translated into predicted dose. We will calculate differences between PET-CT and MAA doses, and present the data graphically. We will use the method proposed by Bland & Altman (2007) to assess the agreement between the two methods. Finally, in a subset of patients, we will explore the change in dose measured by PET-CT scan between day 0 and day 1. The dose at day 1 will be adjusted to account for the decay of the yttrium-90 using  $A=A_0e^{-(0.693t/T_{1/2})}$ . Observed changes in dose may be due to microsphere migration, and our main interest is to look for a systematic change in dose received based on this migration.

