### **1.2 Background**

The current methodology for determining the prescribed dose for patients to be treated with radiolabeled microspheres likely leads to suboptimal treatment of hepatic malignancies, with most patients being either overtreated or undertreated. The development of a novel technique for defining actual dose delivered will better define the activity required to achieve specific doses, and begin to support the transition from a model of dose prescription based primarily on body surface area to one that predicts the dose to both tumor and normal tissues.

The current formulae for determining the prescribed activity to patients to be treated with radiolabeled microspheres are crude and do not take into account significant variations in tumor size, shape, or location. There are two radiolabeled microsphere products currently available for treating patients with liver tumors (metastatic or primary): SIR-Spheres (Sirtex Medical, North Sydney, Australia) and Therasphere (Nordion, Ottawa, Canada). The formula most commonly used for SIR-Spheres is largely driven by body surface area:

$$A \text{ [GBq]} = \text{BSA} - 0.2 + (\text{TV}/\text{TLV})$$

where A = activity, GBq = Gigabecquerels (units), BSA = body surface area, TV = tumor volume, and TLV = total liver volume. This may be multiplied by the lobe factor (fraction of the total liver volume being treated) for patients in whom whole liver treatment is not being pursued. The formula used for calculation of activity in Therasphere administration is:

$$A \text{ [GBq]} = (\text{D [Gy]} \times \text{m [kg]})/49.38$$

where D is the desired dose in Gy, m is the tumor mass in kg. Dose is set to a nominal 100-120 Gy, based on an expected uniform distribution of microspheres over the treated region. However, there is no data available to date that would definitely confirm this. Moreover, this should not be expected to be true. This is due to the existence of hypervascular malignancy with blood supply derived from the hepatic arterial system and normal tissue deriving its blood supply from the portal vein—all within the treated volume.

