### **4.0 Patient Selection Inclusion & Exclusion**

#### **4.1 Inclusion Criteria**

- 4.1.1 Patients must be at least 18 years of age.
- 4.1.2 Patients must have liver-dominant or liver-only metastatic disease from any primary histology. Patients with primary hepatocellular or biliary cancer are also eligible.
- 4.1.3 Patients must be clinical candidates for radioembolization with either SIR-spheres or Therasphere due to metastatic or primary malignancies of the liver.
- 4.1.4 Women of child bearing potential must have a negative serum pregnancy test no more than 72 hours prior to registration.
- 4.1.5 ECOG performance status (PS) of 0, 1 or 2.
- 4.1.6 Ability to understand and willingness to sign a written informed consent and HIPAA authorization for release of medical information.
- 4.1.7 Complete Blood Count (CBC), Chemistry Panel (CMP) and Coagulation Panel (PT, & INR) no greater than 4 weeks prior to registration.
- 4.1.8 Diagnostic imaging of the abdomen utilizing either CT with contrast, MRI, or PET/CT no greater than 6 weeks prior to registration.

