#### Sample size considerations

We will power our study to detect a 10 Gy difference in mean radiation doses between tumors with local control and 6 months vs those which progressed. Based on preliminary data, we expect that the standard deviation of doses will be 12Gy, and that approximately 60% of tumors will retain local control at 6 months. We will use a two-sided test with type I error of 0.05. In preliminary data, within-patient correlation was 0.6-0.7, and we saw an average of 2 tumors per patient. We therefore will enroll 43 patients in this study to have approximately 80% power to detect a difference of 10 Gy.

It is anticipated that 10 patients will be recruited for Day 1 PET-CT studies. This number of patients would be expected to detect a difference in the range of 12-20 Gy (Day 0 – Decay-adjusted day 1). Although we may not get a significant result, the point estimates may give an indication of whether the microspheres are moving. This level of certainty is felt to be appropriate for an exploratory aim.

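### Does it matter that Section 8.0 does not say whether the unadjusted or the adjusted dose coefficient is tested at 0.05?

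*Combined protocol and SAP*

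**What the plan says.** Section 8.0 plans a tumour-level analysis of dose and 6-month local control by "regression models with Generalized Estimating Equations (GEE) to account for within-patient correlation". The next sentence reads: "We will use logistic regression to adjust for potentially confounding factors such as tumor volume, primary histology, and SIR-Spheres versus Therasphere intervention". The link function, the working correlation and the histology categories are not given.

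The sample-size paragraph states "We will use a two-sided test with type I error of 0.05" and "We will power our study to detect a 10 Gy difference in mean radiation doses", comparing controlled with progressed tumours. No covariate enters that calculation.

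Two other places bear on the point. Section 4.1 says "Patients must have liver-dominant or liver-only metastatic disease from any primary histology", and also admits primary hepatocellular and biliary cancer. Section 1.2 describes different activity rules for the two products: "The formula most commonly used for SIR-Spheres is largely driven by body surface area", while for Therasphere "Dose is set to a nominal 100-120 Gy, based on an expected uniform distribution of microspheres over the treated region".

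**The concern.** Dose is not randomised here, so adjustment can change the question and not only the precision. Section 1.2 gives a reason to expect dose to differ by product. If product is also related to control, an unadjusted and an adjusted dose coefficient estimate different things and can differ in significance. The power basis points to an unadjusted comparison, while the confounder sentence points to an adjusted one. If the model and the histology grouping were picked after outcomes were seen, the nominal 5% would become the error rate of the best of several tests on the primary objective.

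**Working it through.** **1. The plan's own figure.** Inputs from the sample-size paragraph: difference 10 Gy, SD 12 Gy ("we expect that the standard deviation of doses will be 12Gy"), 60% controlled, two tumours per patient, within-patient correlation ρ = 0.6–0.7, 43 patients, two-sided 0.05.

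- Independent progressed tumours for 80% power: (1 + 1/1.5) × [12 × (1.960 + 0.842)/10]² = 18.84. Total tumours: 18.84 × 2.5 = 47.1.
- Patients: 47.1 × (1 + ρ)/2 = 37.7, 38.9 and 40.0 at ρ = 0.6, 0.65 and 0.7. With a t reference the numbers are 40, 41 and 42.
- Effective tumours with 43 patients: 86/(1 + ρ) = 53.8, 52.1 and 50.6. Power is 84.9%, 83.8% and 82.7% (normal), or 83.6%, 82.4% and 81.2% (t).

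So 43 patients and about 80% power reproduce as a simple comparison of means. That is a conventional planning simplification; it does not by itself create a second, unadjusted primary test.

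**2. Reading the two sentences together.** Local control at 6 months is binary. One sentence supplies the clustering method, and the next supplies the logistic form and the confounders. They describe the same relationship and fit one model. Section 8.0 mentions no separate unadjusted model, and clustering is already covered by the GEE sentence.

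**3. How far the choice could move the error rate.** Two independent tests at 0.05 would give 1 − 0.95² = 9.75%. The two here share the same doses and outcomes. At an assumed correlation of 0.9 to 0.7 between the statistics, the rate is 7.0–8.3%.

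A simulated null took from the plan 43 patients, a mean of two tumours, 60% control, dose SD 12 Gy and dose correlation 0.65. The following were assumed: latent outcome correlation 0.7 or 0.9; cluster sizes all two, or unequal with mean two; products split 50/50 and unrelated to dose; histology 0.5/0.3/0.2. Models were logistic GEEs with the default sandwich, 3,000 data sets per row, simulation SE about 0.5 points. Rejection rates in per cent:

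| Working correlation, cluster sizes, outcome correlation | Unadjusted | Adjusted (3 histology groups) | Either | Either − unadjusted | Either − adjusted |
|---|---|---|---|---|---|
| Exchangeable, equal, 0.7 | 6.1 | 6.8 | 7.9 | 1.8 | 1.1 |
| Exchangeable, equal, 0.9 | 5.0 | 5.5 | 6.8 | 1.8 | 1.3 |
| Exchangeable, unequal, 0.7 | 6.1 | 7.2 | 8.1 | 2.0 | 0.9 |
| Exchangeable, unequal, 0.9 | 4.8 | 6.0 | 6.7 | 1.9 | 0.7 |
| Independence, equal, 0.7 | 6.0 | 7.3 | 8.2 | 2.2 | 0.9 |
| Independence, equal, 0.9 | 5.0 | 6.9 | 7.7 | 2.7 | 0.8 |
| Independence, unequal, 0.7 | 6.5 | 8.6 | 9.7 | 3.2 | 1.1 |
| Independence, unequal, 0.9 | 6.6 | 8.9 | 9.7 | 3.1 | 0.8 |

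Also allowing a two-group histology coding moves the range for claiming any of them only to 6.9–10.1%.

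One caution: 0.9–7.6% of three-group fits failed and were counted as not significant under Either. If the adjusted column leaves them out, applying the largest failure rate to every row gives at most 9.7 − 8.6 × (1 − 0.076) = 1.8 points in the last column.

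**4. Where the rest of the excess comes from.** A three-group adjusted test named in advance already rejects in 5.5–8.9%, which is 0.5–3.9 points above nominal with no choice left. This points to the sandwich variance with 43 clusters. A separate run (independence working correlation, 1,200 data sets per scenario, SE about 0.6 points) agrees: Either was 6.8–11.1% with the default sandwich and 3.8–6.3% with the Mancl–DeRouen correction, with neither test named.

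**5. Power under either choice.** With product and dose unrelated, simulated power at 10 Gy is 84–95% unadjusted and 86–95% adjusted (among fits that converged). A cruder calculation multiplies the effective tumours by 1 − R², where R² is the assumed share of dose variance explained by the covariates. It gives 79–81% at R² = 0.1 and 74–76% at R² = 0.2. Which coefficient has more power depends on the assumptions.

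**The case for a change.** The strongest opposing case is confounding by product. Assume product shifts dose by 6 or 12 Gy, control differs by product (70% v 50% or 66% v 54%), and dose has no effect within product. Then the unadjusted test rejects in 6.8–12.1% of data sets, the adjusted in 5.9–8.9% and either in 9.3–16.0%; the two disagree in 5.1–12.6%. A separate program gave similar values for either (10.6–16.5%) and for disagreement (6.9–12.5%).

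The logic stands, but its size does not transfer to this trial. Section 1.2 gives activity formulas, not tumour doses by product, and none of these shifts or control rates is in the documents. In such data a marginal association between dose and control does exist, so an unadjusted rejection is not plainly a false positive for an objective worded as a relationship. The disagreement is in significance, not in direction. Moreover, product is among the confounders that Section 8.0 already names, and the adjusted test's 5.9–8.9% hardly differs from its 5.5–8.9% without the link.

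The second objection is sparse data. About 0.4 × 86 = 34 progressed tumours, worth 34.4/1.7 to 34.4/1.6 = 20–22 independent ones under the full design effect, cannot support many histology terms. That is true, and it pushes any analyst towards few groups. With any primary eligible, the case mix is unknown when the plan is written. Groups can be formed from baseline frequencies without looking at outcomes.

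**Conclusion.** No change follows. Section 8.0 does leave the primary coefficient unnamed, the covariate list open and the histology groups undefined, but an analyst would fill this sensibly with the adjusted, patient-clustered logistic GEE that its two sentences describe. Under a null with product unrelated to dose, naming that test rather than claiming either lowers the false-positive rate by 0.7–1.3 points (at most 1.8 allowing for failed fits). Naming the unadjusted test lowers it by 1.8–3.2 points. Either gain arises only if someone would otherwise choose after seeing outcomes, which nothing in the document indicates. Much of the adjusted test's excess over 5% is present with a single test fixed beforehand.

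The consequences are also limited: Section 3.0 describes a single-arm registry study to validate a dosimetry method, and no treatment comparison rests on this p-value. The sizes depend on the assumed outcome correlation, cluster sizes, product split and histology mix. A strong link of product to both dose and control would widen the gap between the two coefficients, but the documents give no figure for it.

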Neither one of these formulas, nor any others in routine use, takes into account the differences in expected dose based upon the size, shape, and location of tumors. In fact, the prescription is simply the total activity to be administered, without any calculation of the dose to be delivered from this activity. Additionally, there is almost no calculation of expected normal tissue doses, with the exception of the use of Tc-99m macro-aggregated albumin (MAA) in order to quantify the lung shunt at the time of angiography prior to treatment. These limitations in the current prescription methodology hamper the ability to move this treatment technique forward, because without doses to both normal tissues and tumors it is not possible to ascribe better responses or increased side effects to the doses received. Therefore, in the ten years since this treatment has become available, there has been little or minimal advancement in the treatment technique.

The emission of positrons from Y-90 has recently been used to generate positron emission tomographs of radiolabeled microsphere distribution [3]. A similar technique has been used to measure the absorbed dose in an anatomical phantom – a laboratory stand-in for a patient – after treatment with SIR-spheres [4]. However, to our knowledge this technique has not been routinely performed in patients.

With the availability of a new technique to quantify the dose to tumors and normal tissues, it will be possible to correlate response and toxicity with actual dose delivered. A second potential application will be the correlation of the activity on the MAA scan with the actual dose deposition. It will be valuable to determine whether the MAA scan is a reliable predictor of dose distribution. With this relationship better defined, we may be able to escalate the dose delivered in many patients in order to improve the control rates and decrease doses in patients who are expected to have higher doses to normal tissues.

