### 2.2 Secondary Objectives

- To evaluate the ability of PET-CT to reproducibly determine dose to tumor, normal liver, and other surrounding organs
- To determine the stability of microsphere location by examining the changes in dose in a subset of patients with PET-CT scans performed on Day 0 and Day 1
- To determine the relationship of dose predicted by Tc-99m labeled Macro-aggregated albumin (MAA) imaged using SPECT versus post-treatment dosimetry
- To determine the effect of dose delivered on local control and normal tissue complications
- To measure the perfusion of the tumor for correlation with dose deposition, based on arterial phase CT measurements
- To evaluate overall survival for 5 years after Visit 1, Day 0.

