### **Additional Radioembolization Treatments**

As a part of standard of care, many patients will require a second radioembolization.

Patients requiring a second radioembolization treatment will be scanned additionally at Visit 1 (Day 0) and Visit 2 (Day 1) after the second treatment.

Visit 2 of the second radioembolization will take place on Day 1, and will be pursued in only a subset of patients. This will include only a PET-CT for the purposes of determining the stability of microsphere placement. The Visit 2, Day 1 PET-CT should be scheduled 24 hours +/- 3 hours after the Visit 1, Day 0 post-treatment PET-CT.

In these cases the 1 month follow up visit may be conducted on the day of the second treatment.

Follow up visits may be conducted by any investigator and will include the following studies:

- CBC and CMP will be drawn at each follow-up visit
- Beginning at the 3-month visit, each visit should be accompanied by tumor imaging to evaluate local control. The modality of tumor imaging will be at the discretion of the investigator, but it is encouraged to use the same modality consistently over time.

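### Fatigue, nausea and pain are to be tested against healthy-tissue dose, but the recording rules capture only events related to the PET/CT scans; liver-test elevation also lacks a stated reference to the registration value

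*Combined protocol and SAP*

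**What the plan says.** **The analysis.** Section 2.2 lists as a secondary objective "To determine the effect of dose delivered on local control and normal tissue complications". Section 1.2 gives the same aim as part of the rationale: with the new technique, "it will be possible to correlate response and toxicity with actual dose delivered". Section 8.0 puts it into effect. It names fatigue, nausea, pain and elevated liver function tests as examples, and says each "side effect will be characterized as present or absent, and we will test the relationship between radiation dose" to the matching healthy tissue and that outcome. Its worked example is that "we will look at the relationship between dose to the normal liver and elevation of liver function tests". It gives no grade, cut-off, visit or window, and does not mention the registration value.

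**The recording rules.** Section 7.0 restricts adverse-event recording to events at least possibly related to the Visit 1 and Visit 2 PET/CT scans. Study Calendar note H, attached to the follow-up adverse-event assessment, restricts it to the Day 1 scan. Section 7.2.1 applies the scan-related limit to the CRF. Note G describes a symptom-guided examination at registration and follow-up, but requires no presence or grade to be recorded.

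**The laboratory data.** Section 4.1.7 requires "Complete Blood Count (CBC), Chemistry Panel (CMP) and Coagulation Panel (PT, & INR) no greater than 4 weeks prior to registration" but sets no limit on the liver tests. In Section 5.0, "CBC and CMP will be drawn at each follow-up visit".

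**Second treatments.** Section 5.0 expects that "many patients will require a second radioembolization", and adds: "In these cases the 1 month follow up visit may be conducted on the day of the second treatment". These patients have the Day 0 PET-CT again after the second treatment. Section 8.0 does not say which dose is paired with a later outcome.

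**The concern.** A symptom can be tested against dose only if it was recorded whether or not anyone blamed the scan. The symptoms of interest are those that might come from irradiating healthy tissue. An investigator who attributes nausea to the radioembolization and not to the imaging would, under these rules, leave it off the form. Section 8.0 asks for an analysis of data that Sections 6.0 and 7.0 do not collect, and unrecorded symptoms may not be recoverable from clinic notes later.

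The liver tests are a lesser matter, because the laboratory values are drawn regardless of the adverse-event rule. The variable, however, is not defined. In patients with liver metastases or primary liver cancer and no eligibility limit, some tests may already be raised at registration. The plan does not say whether such a patient counts as having the side effect, which visit is used, or how a second treatment enters. Those choices could then be made after the data are seen.

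**Working it through.** **1. Side effects against data sources.**

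| Named in Section 8.0 | Source in the documents | Independent of scan attribution? |
|---|---|---|
| Fatigue | Adverse-event form (Sections 7.0, 7.2.1; note H) | No |
| Nausea | Same | No |
| Pain | Same | No |
| Elevated liver function tests | Chemistry at registration and each follow-up | Yes, if the panel contains the liver tests |

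Three of the four depend on the scan-related form. The calendar's adverse-event assessment begins at Visit 1, so that form also gives no registration status for symptoms. The examination in note G takes place at both times but has no recording requirement. As written, either there are no usable symptom data, or the only symptoms counted are those attributed to a scan, which is not the outcome the objective needs.

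The recording rules also differ among themselves. Note H covers the Day 1 scan, Section 7.0 both scans. Section 7.0 stops following events at resolution or 30 days after Visit 2, a visit only a subset attends. Section 7.2.1 records until resolution.

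**2. The plan's own figure.** There is none for the side-effect tests. For the primary comparison, the inputs in Section 8.0 are a 10 Gy difference, SD 12 Gy, 60% controlled, two-sided 0.05, 80% power, 2 tumors per patient and correlation 0.6 to 0.7. The smaller group needs (1.96 + 0.842)² × 12² × (1 + 1/1.5) / 10² = 18.8, so 19, and 19 × 2.5 = 47.5 tumors in all. Patients = 47.5 × (1 + correlation) / 2, which is 38 at 0.6 and 41 (40.4 rounded up) at 0.7. A t-based version gives 40 to 42. The planned 43 stands, and nothing here alters it.

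**3. Liver tests: what dichotomising could cost.** Under a normal model, a present/absent outcome with proportion p present keeps φ(c)² / [p(1 − p)] of the information in the continuous value, where φ is the normal density at the cut-off c. At p = 0.5 this is 0.1592 / 0.25 = 0.64, so 43 patients act like about 27. At p = 0.1 it is 0.34, or about 15.

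**4. Simulated power (illustrative).** Only n = 43 comes from the documents. Assumed: 20%, 35% or 50% above the cut-off at registration; registration-to-follow-up correlation 0.5 or 0.7; an effect of 0.35 SD per SD of dose; 2,000 runs per combination; Wald logistic or linear regression.

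| Analysis | Base inputs | With dose-unrelated rises |
|---|---|---|
| Present/absent, no registration value | 25–39% | 20–28% |
| New or worsened (above the cut-off, and newly so or risen by at least 0.5 SD) | 22–43% | 19–29% |
| Continuous, registration value as covariate | 69–87% | 28–33% |

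The last column adds rises unrelated to dose, such as tumor progression might cause, in 30% of patients (exponential, mean 2 SD, assumed). Compared within each combination, the gain of the continuous model over present/absent is 33 to 56 points with the base inputs (smallest 0.691 − 0.364, largest 0.850 − 0.286). With the added rises it is about 1 to 12 points.

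**5. Simulated false positives, no dose effect.** Present/absent gives 3–4% when the registration value is unrelated to normal-liver dose, 5–8% at correlation 0.15 and 8–18% at 0.3. New or worsened gives 2–5% throughout at the 0.5 SD rise, and the continuous model 5–6%.

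**The case against.** On symptoms, one can say that the examination in note G will leave notes, that Section 9.1 has all patient information stored for analysis, and that the list in Section 8.0 is only illustrative. This softens the point without removing it. None of these passages requires symptom presence or grade to be captured, and note H restricts the assessment that might have done so. It also stands that rewriting the wording of Section 7.2 would be the wrong remedy. The same scan-related limit governs 24-hour SAE, IRB and MedWatch reporting there, so loosening it could widen safety reporting.

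On liver tests, the other side is stronger. The objective concerns complications, and present/absent answers that directly; a shift in a laboratory value is a different question. The power gain depends on the assumed model, as step 4 shows. Defining the outcome as new or worsened has its own cost: if a rise of 1.0 SD is required, power at 0.35 SD falls to 22–31%. These points stand, and they are why the continuous model is proposed only as support.

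A reader might go further and infer that the plan ignores the registration value, or counts pre-existing abnormality as a side effect. The documents do not support that: Section 8.0 is silent, and elevation can be read as change after treatment. Nor do they show that false positives are inflated, which needs registration abnormality to be related to normal-liver dose. A reader might also infer that second treatments would spoil the analysis. Patients are rescanned after a second treatment, so cumulative dose can be obtained; only the pairing rule is missing.

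**Conclusion.** The symptom conflict holds on the text and needs no numerical assumption. Followed as written, the plan leaves three of the four named side effects in a stated secondary analysis without a reliable data source. It should be corrected.

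The liver-test point holds as a lower-priority gap in definition. Referring the result to a registration value already collected costs almost nothing. The continuous model is expected to have more power, but the documents do not supply the inputs that would size the gain, and the simulated percentages are not forecasts for this trial. It is also assumed that the chemistry panel contains the liver tests; the documents do not list its components.

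It would be wrong to conclude that the trial's main result is at risk. This is a secondary analysis with no stated power, and the primary analysis and sample size are unaffected.

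**What to change.** **Symptoms (protocol and CRF).** Reconcile Section 8.0 with Study Calendar note H and Sections 7.0 and 7.2.1 by adding a separate CRF item. It grades fatigue, nausea and pain at registration and at each follow-up visit, whatever the attribution. State that this item feeds the Section 8.0 analysis and leaves the scan-related limit on AE/SAE reporting unchanged. Analyse each symptom as new or worsened from registration. Bring note H and Sections 7.0 and 7.2.1 into line with each other at the same time. Cost: a small CRF addition and some data entry, at visits where the examination already takes place.

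**Liver tests (Section 8.0 wording).** Name the tests. Define elevation as new or worsened from registration at one prespecified visit, with the cut-off and the minimum rise stated. Pair the result with first-treatment dose if the sample precedes any second radioembolization, and with cumulative dose if it follows. Where the 1-month visit falls on the day of the second treatment, say which case applies. Add a supporting regression of the log follow-up value on normal-liver dose, with the log registration value as covariate. Cost: a few sentences and one more model, whose result is less clinically direct than the occurrence of a complication; no new blood draws if the panel contains the tests.
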